#### **Data:**

We will use Covered California administrative data to obtain enrollment outcomes and baseline demographics for our sample and health care claims database to obtain health care utilization and financial outcomes.

We will use data from the Department of Health Care Access and Information for hospital admissions data for all individuals in the intervention. We will use data from the California Franchise Tax Board to measure which individuals reported not having Minimum Essential Coverage (MEC) while filing their state taxes.

#### **Quality Control Checks:**

After carrying out the randomization, we will check for balance across several observable covariates (e.g., gender of head of household, presence of email address on the application,

---

 Authors' calculations based on a two-sample proportion Pearson's chi-squared test using Stata 18 SE software

age, and income as a percent of the federal poverty level), which could indicate that there would be no significant dissimilarities across treatment arms.

### **Statistical Models**

**Intention-to-treat estimation:** To estimate treatment effects, our primary analysis will be an intent-to-treat (ITT) specification, examining the effect of treatment assignment. We will estimate the effect of the treatment using ordinary least squares (OLS) regression. That is, we will regress the outcome of interest (e.g., take-up) for household  $i$  on the treatment indicator:

$$\text{outcome}_i = \alpha + \beta_1 \text{Treatment}_i + \varepsilon_i$$

The coefficient  $\beta_1$  will be the intent-to-treat estimate of the causal effect of the outreach.

**Complier average causal effect estimation:** We will examine the effects of health insurance (among households induced to enroll in a Covered California as a result of random assignment) on our four utilization outcomes. We anticipate a significant share of noncompliers among those households assigned to receive outreach (intervention) as they may have opted out of assigned plan or not enroll into another Covered California plan. Thus, to augment our analysis of insurance take-up, we will also estimate treatment effects based on treatment receipt (enrollment into Covered California Plan), using two-stage least squares regression (2SLS).

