### Interventions and Randomization

We evaluate the effectiveness of phone outreach on health insurance take-up among auto-enrolled households given that this is a new population for Covered California.

The project's research design is a block-randomized intervention among automatically enrolled households. We separate households by preferred spoken language and net premium of the assigned health plan and randomly assign households within each on continuous basis to (1) a control group with a standard eligibility notice for auto-enrolled households, or to (2) a treatment group to receive additional phone outreach from Covered California's service center.

*Table 1. Approximate sizes of control and treatment groups for the evaluation*

Cohort month	Control	Treatment
August 2023	750	500
September 2023	1,698	5,365
October 2023	7,466	3,132
November 2023	1,838	4,935
December 2023	487	5457
May 2024	6,696	2,021
June 2024	8,000	2,100
July 2024	8,000	2,100
Total	30,101	29,944

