### Power:

To arrive at an estimate for the minimum detectable effect (MDE) for our primary outcome, we assume a baseline health insurance take up of 6 percent. The baseline rate was determined with the historical data on the plan effectuation of individuals disenrolled from Medi-Cal in 2018-

2022 years. The intervention was powered at the 80% level to detect a 0.6 percentage point increase in effectuation rate.

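### The primary ITT regression has no cohort term although the share assigned to outreach runs from 21% to 92% by cohort month, so β₁ is biased if baseline take-up varies with that share

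*Combined protocol and SAP*

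**What the plan says.** Under Interventions and Randomization, the blocks are language and premium: "We separate households by preferred spoken language and net premium of the assigned health plan". Assignment then ran over time: the plan will "randomly assign households within each on continuous basis". Cohort month is not named as a block. Table 1, titled "Approximate sizes of control and treatment groups for the evaluation", lists eight cohort months with very different control-to-treatment splits.

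Under Statistical Models, the primary analysis is described as follows: "We will estimate the effect of the treatment using ordinary least squares (OLS) regression". The printed equation is outcome = α + β₁·Treatment + ε, and the text says that β₁ "will be the intent-to-treat estimate of the causal effect of the outreach". No section adds cohort terms, block terms, weights or a stratified estimate. The covariates listed under Quality Control Checks are examples, and cohort month is not among them.

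Under Power, one baseline rate serves the whole sample: "we assume a baseline health insurance take up of 6 percent". It comes from 2018-2022 data, and no rate by cohort is given.

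**The concern.** When the assignment probability differs between strata, randomisation identifies the effect within each stratum. A pooled difference in means also picks up any difference in baseline outcome between strata, in proportion to how unevenly the arms are spread over them. Here the treated arm is mostly 2023 households and the control arm mostly 2024 households, so the printed model partly compares years.

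Nothing in the plan supports equal take-up over time. The 6% rate predates the automatic-enrolment programme, the plan itself calls this population new, and the primary outcome is tied to the calendar month of outreach. None of this proves that a gap exists. It does mean that the primary estimate depends on a condition the plan neither states nor supports.

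The results are meant to guide operations and budget. A positive association between take-up and the assigned share would credit the calls with an effect they did not have. A negative one would hide a real effect or make the calls look harmful.

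**Working it through.** **1. The plan's own figure.** A two-sided 5% chi-squared test with a 6% control rate and the stated arms of 30,101 and 29,944 has 80% power at a difference of 0.555 pp, which rounds to the stated 0.6 pp. Power at exactly 0.6 pp is 85.7%. The figure reproduces as a rounded value for an unstratified comparison.

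**2. Shares and loadings from the printed rows of Table 1.** Share to outreach = T/(C+T). Loading = (cohort's fraction of the treated arm) − (its fraction of the control arm). The rows sum to 34,935 control and 25,610 treated.

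| Cohort | Control | Treated | Share to outreach | Loading |
|---|---|---|---|---|
| Aug 2023 | 750 | 500 | 40.0% | −0.002 |
| Sep 2023 | 1,698 | 5,365 | 76.0% | +0.161 |
| Oct 2023 | 7,466 | 3,132 | 29.6% | −0.091 |
| Nov 2023 | 1,838 | 4,935 | 72.9% | +0.140 |
| Dec 2023 | 487 | 5,457 | 91.8% | +0.199 |
| May 2024 | 6,696 | 2,021 | 23.2% | −0.113 |
| Jun 2024 | 8,000 | 2,100 | 20.8% | −0.147 |
| Jul 2024 | 8,000 | 2,100 | 20.8% | −0.147 |

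**3. Bias of the unadjusted β₁.** Bias = Σ loading × cohort baseline take-up. The loadings sum to zero, so equal take-up gives no bias. As an example, take-up 1 pp higher in December 2023 alone adds 0.20 pp.

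If take-up is uniform within each year, only the 2023-minus-2024 gap matters. Its loading is 19,389/25,610 − 12,239/34,935 = 0.757 − 0.350 = 0.407.

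**4. Table 1 does not add up.** The row sums differ from the stated totals of 30,101 and 29,944. Exchanging the two October cells makes the treatment column exactly 29,944 and leaves control at 30,601, which is 500 too many. October's share to outreach is then 70%, the range over all months is unchanged, and the year loading is 23,723/29,944 − 7,905/30,601 = 0.792 − 0.258 = 0.534. Both readings are carried below.

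**5. Rejection rates with no true effect.** Assumptions: take-up of 6% in the 2024 cohorts and 6% plus the gap in the 2023 cohorts; two-sided 5% unpooled z-test. For a +1 pp gap on the printed rows:

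- treated rate 6 + 0.757 = 6.757%; control rate 6 + 0.350 = 6.350%; difference 0.407 pp
- SE = √(0.06757×0.93243/25,610 + 0.06350×0.93650/34,935) = 0.204 pp
- z = 1.99, so the test rejects 51.3% of the time

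| Assumed gap (pp) | Bias, printed (pp) | Rejects, printed | Rejects, October exchanged |
|---|---|---|---|
| −1.5 | −0.61 | 92.0% | 99.3% |
| −1 | −0.41 | 58.9% | 82.3% |
| −0.5 | −0.20 | 18.7% | 29.2% |
| 0 | 0 | 5% | 5% |
| +0.5 | +0.20 | 17.5% | 27.3% |
| +1 | +0.41 | 51.3% | 75.8% |
| +1.5 | +0.61 | 83.4% | 97.5% |
| +2 | +0.81 | 97.0% | 99.9% |

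Simulation of 20,000 trials at each positive gap agreed for the printed rows (17.1, 51.1, 83.6 and 97.3%). With cohort strata in the analysis, the simulated rate was 4.7% to 5.2% at every gap.

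**6. Chance of a significant positive result when the true effect is 0.6 pp.** On the printed rows it is 85% at zero gap and 52, 17 and 2% at gaps of −0.5, −1 and −1.5 pp.

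**7. Precision of the adjusted estimate.** Unadjusted information is 34,935×25,610/60,545 = 14,777. With cohort fixed effects it is Σ C·T/(C+T) = 300 + 1,290 + 2,206 + 1,339 + 447 + 1,552 + 1,663 + 1,663 ≈ 10,462. The variance ratio is 14,777/10,462 = 1.41 (1.45 with October exchanged).

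The detectable effect solves δ = (1.960 + 0.842)·SE(δ), with a 6% control rate, a constant effect and variance under the alternative:

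| Analysis | Detectable at 80% power | Power at 0.6 pp |
|---|---|---|
| Unadjusted | 0.56 pp | 85% |
| Cohort fixed effects | 0.67 pp | 71% |
| Weighted to cohort size | 0.70 pp | 68% |

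**The case against.** The strongest reply is that the harm is conditional. Every gap above is assumed, and with no gap the printed model is unbiased and more precise than the adjusted one. Bias also needs more than some difference between cohorts: take-up must vary with the assigned share. Higher take-up in October 2023 alone would lower β₁ on the printed rows, not raise it. All of this stands. It means that the documents show an unprotected estimator, not a biased result, and that the year-gap figures hold only under take-up that is uniform within year.

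Table 1 is also a weak base for exact numbers. It is labelled approximate, its rows contradict its totals, and its July 2024 row postdates the document's update of June 5, 2024, so it cannot be a final count. This limits the precision of the figures but not the conclusion. No plausible rounding turns 92% and 21% into one common share, and the one exchange that repairs the treatment total makes the imbalance between years worse.

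Finally, the plan gives no assignment shares by language or premium block, so imbalance on those variables is not shown. The point rests on cohort month alone. The loss of power under adjustment is real, but the higher unadjusted power is valid only if the cohorts do not differ.

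**Conclusion.** The concern holds. Followed as written, the primary analysis mixes any cohort difference in take-up that tracks the assigned share with the effect of the calls, and nothing else in the plan corrects this. That the term is missing is certain from the text; the size and sign of any bias are not.

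Under take-up uniform within year, each 1 pp of gap between 2023 and 2024 moves β₁ by 0.41 pp on the printed rows, or 0.53 pp with October exchanged. A gap of about 1.5 pp (0.6/0.407) produces a bias as large as the 0.6 pp design effect. Gaps in either direction break the 5% error rate. A larger sample with the same shares would not reduce the bias. Because this is the only printed primary model, it must be changed, and the change should be fixed before outcomes are analysed.

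**What to change.** Replace the primary model with outcome = α + β₁·Treatment + γ_b + ε, where γ_b are fixed effects for cohort month crossed with the language and net-premium blocks. The following should be stated with it.

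- **Thin cells.** December 2023 has only 487 controls. A crossed cell with one arm only adds nothing to β₁. If sparse cells are to be simplified, give the minimum cell size in advance, always keep the cohort-month effects, and enter language and premium as main effects. That fallback need not remove imbalance between blocks within a month, so the shares by block should be reported.
- **Other analyses.** Put the same terms into both 2SLS stages, the subgroup models and the balance checks.
- **Target of estimation.** Fixed effects weight cohorts by C·T/(C+T). December 2023 then gets 447/10,462 = 4.3% of the weight but holds 5,944/60,545 = 9.8% of households. An estimate weighted to cohort size, using inverse-probability weights from the actual cohort shares, can be a sensitivity analysis. It targets a different average if effects vary by cohort, and its variance is about 1.53 times the unadjusted one.
- **Table 1.** Reconcile its rows and totals, and replace approximate counts with actual ones, since the weights depend on them.
- **Power.** The plan says "The intervention was powered at the 80% level to detect a 0.6 percentage point increase in effectuation rate". With cohort fixed effects, restate this as about 0.67 pp at 80% power, or about 71% power at 0.6 pp, updated for the reconciled counts. The further effect of crossing with the blocks cannot be computed without block shares.

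The cost is SAP wording and a restated power figure. Cohort month, language and net premium are already held as assignment variables, so no new data are needed.

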### **Inference Criteria, Including Any Adjustments for Multiple Comparisons:**

We will not perform any corrections for multiple hypothesis testing, and we will use two-tailed tests with p-values  $\leq 0.05$  to denote statistically significant effects.

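### Low-priority free improvement: the outcome model contains only the treatment indicator, although four baseline covariates are already named and could be pre-specified in it for a small gain in precision

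*Combined protocol and SAP*

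**What the plan says.** Under Statistical Models, the intention-to-treat analysis is ordinary least squares: "we will regress the outcome of interest (e.g., take-up) for household" i on treatment. The printed equation has an intercept, the treatment indicator and an error term. It has no baseline covariates, and no adjusted model is given as a sensitivity analysis. The 2SLS paragraph names no covariates either.

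The Data section says: "We will use Covered California administrative data to obtain enrollment outcomes and baseline demographics for our sample". Under Quality Control Checks, "we will check for balance across several observable covariates", with gender of the household head, email on the application, age and income relative to the federal poverty level given as examples. No test, threshold or consequence is attached to that check.

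The Pre-Specified Subgroup Analyses section uses gender, income group and age bracket again, as subgroup variables for both the intention-to-treat and the complier analyses.

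On power, "we assume a baseline health insurance take up of 6 percent", and the study is "powered at the 80% level to detect a 0.6 percentage point increase in effectuation rate". The footnote to that sentence attributes the figure to a "two-sample proportion Pearson's chi-squared test using Stata 18 SE software", which uses no covariates.

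**The concern.** If age, income, gender or email status predicts take-up, tenure or utilization, leaving it out puts explainable variation into the error term. The standard error is then larger than it need be, with data the plan already intends to obtain.

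There is also a question of discretion. The balance list is open-ended, because it is given by example, and nothing says what follows if a covariate looks unbalanced. An adjusted analysis chosen after seeing the balance table would not be pre-specified. The plan was created in March 2024, after the five 2023 cohorts in Table 1, and the primary outcome is read at the end of the outreach month. A fixed covariate rule, with the unadjusted result beside it, leaves less room for a suspicion of later choice. Most secondary outcomes are measured one to two years on, so for those the rule can still be set before the data are available.

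**Working it through.** **Inputs from the documents.** Control take-up 6%; effect 0.6 percentage points (pp), so 6.0% against 6.6%; two-sided 0.05; printed totals of 30,101 control and 29,944 treatment households; monthly counts in Table 1. **Assumed:** R-squared (R²) of the covariates, 1% to 10%, because the documents give none.

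**The plan's own figure.** With the pooled-variance two-proportion formula and the printed totals, the minimum detectable effect at 80% power is 0.555 pp, which rounds to the stated 0.6. At exactly 6.0% against 6.6%:

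- pooled rate = (30,101 × 0.06 + 29,944 × 0.066) / 60,045 = 0.0630
- standard error (SE) = √(0.06 × 0.94/30,101 + 0.066 × 0.934/29,944) = 0.198 pp; the pooled SE is also 0.198 pp
- power = Φ((0.600 − 1.96 × 0.1983)/0.1983) = Φ(1.066) = 85.7%

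**Cohort-stratified comparison.** Sum n₁n₀/(n₁+n₀) over the eight monthly rows: 300 + 1,290 + 2,206 + 1,339 + 447 + 1,552 + 1,663 + 1,663, which is 10,462 before rounding of the terms. Ignoring cohort, the same rows give 34,935 × 25,610/60,545 = 14,777. Then z = 0.006/√(0.063 × 0.937/10,462) = 2.526, and power = Φ(2.526 − 1.96) = 71.4%.

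**Effect of adjustment.** The SE is multiplied by √(1 − R²). The equivalent number of extra households is 60,045 × (1/(1 − R²) − 1).

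| R² (assumed) | Fall in SE | Equivalent extra households | Power, printed totals, no stratification | Power, cohort-stratified |
|---|---|---|---|---|
| 0% | – | – | 85.7% | 71.4% |
| 1% | 0.5% | about 600 | 86.0% | 71.9% |
| 2% | 1.0% | about 1,200 | 86.4% | 72.3% |
| 5% | 2.5% | about 3,200 | 87.4% | 73.6% |
| 10% | 5.1% | about 6,700 | 89.1% | 75.9% |

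**What R² is plausible?** For a binary covariate with share q and a take-up gap g, R² = q(1 − q)g²/[p(1 − p)]. These gaps are illustrations, not document figures.

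- Even split, 2 pp gap: 0.25 × 0.02²/(0.063 × 0.937) = 0.2%
- Even split, 5 pp gap: 0.25 × 0.05²/(0.063 × 0.937) = 1.1%
- One third at 12%, two thirds at 3%: (2/9) × 0.09²/(0.06 × 0.94) = 3.2%

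Only the part of R² beyond cohort, language and net premium counts in a model that already holds those terms, so the lower rows of the range are the safer guide.

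**Could adjustment restore 80% after stratification?** That needs z = 1.96 + 0.84 = 2.80, so 1 − R² = (2.526/2.80)² = 0.81. About 19% would be required, well above the assumed range.

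**Chance imbalance.** For a covariate with 50% prevalence, the 95% range of the difference between arms is ±1.96 × √(0.25 × (1/30,101 + 1/29,944)) = ±0.8 pp. With a 5 pp take-up gap (assumed), the estimate moves by 0.008 × 5 = 0.04 pp, against an SE of 0.198 pp.

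**The case against.** The strongest case against is that nothing is wrong here. An unadjusted intention-to-treat comparison is valid and already fixes the estimator. The gain is small, it rests on an R-squared that the documents do not supply, and it has been sized for the primary outcome only. All of that stands, and it is why this is an optional improvement.

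Four stronger readings are tempting, and the documents do not support them.

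- *The four covariates serve only the balance check.* Age, income and gender are also pre-specified subgroup variables; of the four, only email has no other stated use. Race and ethnicity and mixed eligibility are named for subgroups and are not among the balance examples.
- *Leaving out covariates underpowers the study.* The model as written has about 86% power at 0.6 pp, above the stated 80%. The 71.4% comes from a treated share that runs from 20.8% to 91.8% across the monthly cohorts, and arises in a stratified model that the plan does not contain.
- *An imbalance would bias the result.* Under valid randomization a chance imbalance does not bias the unadjusted estimate, and at this sample size any shift is likely to be small.
- *There is a 19% chance of a false alarm in the balance checks.* That is 1 − 0.95⁴ = 18.5%, for four independent tests at 0.05. The plan fixes neither the list nor a threshold for these checks; its 0.05 rule concerns treatment effects.

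It is also fair to say that naming covariates without coding them would leave discretion in place. The fix therefore has to settle the coding.

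**Conclusion.** The point holds as a low-priority efficiency and pre-specification improvement. None of the four named covariates enters the equation that estimates the treatment effect, and including them would reduce the SE by about 0.5% to 5.1% for an assumed incremental R-squared of 1% to 10%. Power at 0.6 pp would rise by 0.3 to 3.4 points on the printed totals (from 85.7%), or by 0.5 to 4.5 points in a cohort-stratified comparison (from 71.4%).

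The direction is secure; the size depends on the assumed R-squared and on take-up near 6%. No size is claimed for the secondary outcomes. The stratified figures use the Table 1 rows, which sum to 34,935 and 25,610 rather than the printed 30,101 and 29,944; the two need reconciling, but unstratified power barely changes (85.2% on the summed rows). The cohort-allocation shortfall is a separate matter and remains after this change.

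**What to change.** In Statistical Models, state that the intention-to-treat model for the primary and secondary outcomes, and both stages of 2SLS, will include gender of the household head, email on the application, age and income relative to the poverty level, in addition to cohort-month and randomization-block terms. Say that this applies whatever the balance checks show, and that the unadjusted estimate will be reported alongside.

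Fix the coding in the same place: for example, age of the household head in the subgroup age brackets, income in the subgroup poverty-level groups with their cut-points written out, and a missing-value category. The age brackets as printed leave age 50 in no group, which should be settled at the same time. Date the change, and state whether outcomes for completed cohorts had been seen by then.

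The cost is a few sentences and no new data collection. The downside is the missing-value category that may be needed where a covariate is blank.

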### **Likely Effect Size:**

Based on prior phone outreach campaigns carried out by Covered California, we would expect to observe an ITT effect between 0 and 4 percentage points.

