### ***Data and Data Structure***

#### **Outcomes:**

We use Covered California administrative data to examine health insurance take-up behavior and health care utilization among households included in the study.

The primary outcome of interest will be a binary indicator for whether a consumer is effectuated into Covered California plan, either the plan assigned through the auto-enrollment process, or into another plan chosen by the consumer by the end of the month at which outreach was conducted.

Our secondary outcomes will be measured 1-2 years after the intervention when data becomes available will include:

1. Tenure with Covered California (measured in months);
2. A binary indicator for whether someone had an office visit during 1-2 years since the intervention;
3. A binary indicator for whether someone had a prescription drug fill during 1-2 years since the intervention;
4. A binary indicator for whether someone had an emergency room visit during 1-2 years since the intervention;
5. A binary indicator for whether someone had a hospital admission 1-2 years before and 1-2 years after the intervention.
6. Total out-of-pocket spending for the 1-2 years since the intervention
7. A binary indicator for whether someone self-reported being uninsured while filing their taxes;

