### **Pre-Specified Subgroup Analyses**

We will examine treatment heterogeneity by race and ethnicity of the head of household, written or spoken language, gender of head of household, income group measured by the percentage of the federal poverty level, net premium of assigned plan, age bracket (30 years and younger, 31-49 years old, older than 50 years old), health status as measured by HCIAI discharge data, mixed eligibility household status. Same subgroup analyses will be performed for our complier average causal effect analysis.

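### The planned 2SLS insurance effects on office visits, drug fills and ER visits use a claims source of unstated coverage, so enrollment can raise recorded use without any change in care.

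*Combined protocol and SAP*

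**What the plan says.** In the combined protocol and SAP, the complier average causal effect paragraph of Statistical Models reads: "We will examine the effects of health insurance (among households induced to enroll in a Covered California as a result of random assignment". It applies this to four utilization outcomes and says the analysis will "estimate treatment effects based on treatment receipt (enrollment into Covered California Plan), using two-stage least squares regression (2SLS". The four are not named there. The binary use outcomes listed under Outcomes are office visit, prescription fill, emergency room visit and hospital admission, and I take these to be the four.

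The sources are described unevenly:

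- Hospital admissions come from a state department, "for hospital admissions data for all individuals in the intervention".
- Other use and spending come from a "health care claims database to obtain health care utilization and financial outcomes" (Data section). The database is not named.
- The Outcomes section describes the source differently: "We use Covered California administrative data to examine health insurance take-up behavior and health care utilization among households included in the study".

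No section says which payers or people the claims database covers, or how a person with no record is coded. Pre-Specified Subgroup Analyses adds: "Same subgroup analyses will be performed for our complier average causal effect analysis".

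**The concern.** A claims database records care only when a payer it covers is billed. Enrollment in a Covered California plan is the treatment variable in 2SLS, and it may also decide whether a person's care is seen. Randomisation does not separate the two: assignment raises enrollment, and enrollment raises both recording and, possibly, care. For office visits, fills and ER visits, the estimate labelled as an effect of insurance would then combine care received with care recorded, and the plan gives no means of telling them apart.

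The subgroup versions inherit the problem, because groups that differ only in usual use or in capture would appear to respond differently to insurance. The ITT estimates for these outcomes and for out-of-pocket spending remain valid comparisons of what the source records. They are not comparisons of care received or total cost.

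**Working it through.** The plan gives no figure for any utilization outcome, so there is none to reproduce here. Its only power statement concerns take-up: "powered at the 80% level to detect a 0.6 percentage point increase in effectuation rate". With the printed totals (30,101 control, 29,944 treatment), a 6% baseline and two-sided 0.05, the detectable difference at 80% power is 0.555 points, which rounds to 0.6. That figure does not bear on the artefact.

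**Inputs**

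- From the documents: the 2SLS treatment variable, the data sources, and take-up gains g of 0.6 points (Power) and up to 4 points (Likely Effect Size: "we would expect to observe an ITT effect between 0 and 4 percentage points"). Both gains refer to take-up by the end of the outreach month and are borrowed here.
- Assumed: u, compliers' use rate if not enrolled; u1, their use rate if enrolled; c, the share of non-enrolled use that the source records. The documents give none of these.

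**Conditions.** (a) People without records are coded as no use. (b) Enrollment is measured over the claims window. (c) Enrolled care is fully recorded.

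**Step 1: the 2SLS artefact.** Compliers' recorded use is u1 if enrolled and c × u if not, so

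2SLS = u1 − c·u = (u1 − u) + u(1 − c).

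The first term is the true effect and the second is the artefact. The result does not depend on arm sizes or on the size of the first stage.

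| Case | c = 0 | c = 50% | c = 75% | c = 100% |
|---|---|---|---|---|
| u1 = u = 60% (true effect 0) | +60 | +30 | +15 | 0 |
| u1 = 60%, u = 40% (true effect +20) | +60 | +40 | +30 | +20 |

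Entries are the 2SLS value in percentage points. At c = 0, an assumed u of 10% gives an artefact of +10 and an assumed u of 80% gives +80.

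**Step 2: relaxing (c).** If only a share t of enrolled users have a use recorded during their enrolled spell, and the rest are captured at c, recorded use if enrolled is u[t + (1 − t)c]. Subtracting c·u leaves an artefact of u·t·(1 − c). With u = 60%, c = 0 and t = 0.5 (assumed), that is 0.60 × 0.5 = +30 points. Tenure in months is itself an outcome, so spells of varying length are expected.

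**Step 3: relaxing (b).** Suppose enrollment is fixed at the end of the outreach month, the only date the plan attaches to effectuation, and half of control compliers enroll later (assumed). The artefact halves: 0.60 × 0.5 = +30 points at c = 0.

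**Step 4: ITT on recorded use.** The artefact is u(1 − c) × g. At u = 60% and c = 0 it is 0.60 × 0.006 = 0.36 points for a 0.6-point gain, and 0.60 × 0.04 = 2.4 points for a 4-point gain. With no gain in enrollment there is no ITT artefact.

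**Step 5: false significance, one conditional example.** Assume no true effect, u = 60%, 6% of controls enrolled, g = 0.6 points and the printed totals.

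- At c = 0, recorded use is 0.06 × 0.60 = 3.60% against 0.066 × 0.60 = 3.96%. The standard error is √(0.036 × 0.964/30,101 + 0.0396 × 0.9604/29,944) = 0.156 points, so z = 0.36/0.156 = 2.31 and the ITT test rejects about 64% of the time.
- At c = 50%, recorded use is 31.80% against 31.98%, z is about 0.47, and rejection is about 8%.

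I do not use 2SLS rejection rates as evidence. The first-stage F here is 0.006²/[0.06 × 0.94/30,101 + 0.066 × 0.934/29,944] = 9.2, so the ordinary 2SLS test is distorted by a weak instrument, which is a separate matter.

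**Step 6: subgroups.** With assumed u of 40% and 70% in two groups and no true effect in either, the complier contrast is 70 − 40 = 30 points at c = 0 and 35 − 20 = 15 points at c = 50%.

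The rows of Table 1 sum to 34,935 and 25,610, not to the printed totals. That affects only Step 5 and the power check, where the detectable difference becomes 0.558 points.

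**The case against.** The strongest objection is that the documents establish an omission, not a bias. The database is unnamed, and if it captured everyone's care equally, c would be 1 and the artefact zero. A reader might infer from the reference to Covered California administrative data that the source holds enrollees only, and hence that the 2SLS estimates would be pure artefact. The documents do not support that: the Data section separately mentions a claims database and does not limit it to enrollees. Nor is +60 points an expected bias. It needs the extreme capture value, an assumed use rate and all three conditions.

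These points stand, and they limit the size of the claim. They do not remove it. Even a multi-payer claims source misses care that produces no claim, such as self-pay care by uninsured people, so full capture cannot simply be assumed. The plan claims coverage of all individuals for admissions and for no other use outcome.

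Two further objections are fair. Dropping people without records would condition on something that happens after randomisation, but nothing suggests the authors intend it: the ITT model is written on assignment and the Outcomes text refers to all households in the study. Also, the project's stated question is whether outreach raises take-up, and these outcomes are secondary.

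**Conclusion.** The concern holds in conditional form and should be fixed. For three of the four complier analyses (office visits, fills, ER visits) and their subgroup versions, the plan would present as an effect of insurance an estimate that may include a recording difference, with no stated way to judge how much.

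The artefact is u(1 − c) under conditions (a) to (c), and the illustrated sizes are upper bounds with respect to the departures in Steps 2 and 3. The direction rests on people without records being coded as no use and on capture being incomplete for people who do not enroll. The size rests on u and c, which the documents do not give. Confidence is medium, because the coverage of the source is unknown.

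A reader might extend this to the trial's main result. That would be wrong: primary take-up, tenure, hospital admissions and tax-reported uninsurance do not depend on this claims source. Out-of-pocket spending is not among the 2SLS outcomes, so for spending only the labelling of the ITT result is at issue.

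**What to change.** 1. State which payers and persons the claims source covers, and how people without records are coded. Reconcile the two descriptions of the utilization source in the Outcomes and Data sections.
2. Reserve 2SLS insurance effects, including subgroup versions, for hospital admissions and any outcome from a source shown to capture care regardless of enrollment.
3. For the other claims-based outcomes, including out-of-pocket spending, report ITT, labelled as use or spending recorded in the claims source.
4. If 2SLS is kept for office visits, fills or ER visits, show it only as a sensitivity analysis over assumed capture shares (for example 50%, 75% and 100%), and define when enrollment is measured.

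If the answer to item 1 shows capture that does not depend on enrollment, item 2 lets the planned 2SLS stand. The cost is three or four sentences, with no new data and no change to the primary analysis. The downside is that fewer secondary outcomes may carry a causal claim.
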